## 1. Local Number of Participants

1. Local Number of Participants to be Consented: 100

## **1. Local Recruitment Methods**

1. Recruitment Process: Participants recruited under the Consortium of Addiction Research (CAR) registry and referred to this study will be recruited. CAR research staff will give qualifying participants the “1406M51241 Invite,” which provides a brief study description, a study appointment time, and a Consent Form to review before their appointment if they are interested in completing the study.
2. If participants cannot make it to the appointment but do wish to learn more about the study, they are instructed to return the note requesting another appointment date. If participants do not show up at the appointment time and no note is returned, research staff will assume they are not interested in the study and will not try to look for them.
3. If participants do show up to their appointment, research staff will give them detailed information about the study. If participants are still interested in participating in the study after learning all details of the study, research staff will ask them if they would like to answer confidential questions to confirm that they qualify to be in the study.
4. If participants do not qualify to be in the study, research staff will thank them for their time. . If participants do qualify to be in the study, research staff will let them know that they do qualify to be in the study and ask them if they are still interested to be in the study. If so, research staff will proceed (e.g. consent, HIPAA, etc).
5. When a subject arrives for their first study appointment they will complete a consent process. A trained and IRB-approved study staff person will carry out the process. The study staff person will describe the study, consent form, and the required signatures if the individual agrees to commence with the study. Then the subject will be given time to read the consent form and ask questions of study staff. If the subject agrees they will sign the consent form with the study staff person looking on. Part of the consent involves asking questions of the subject and having him or her record their responses to ensure they understand the study and that they can terminate participation at any point. They are also informed that study staff may terminate study participation at any point if they are concerned about the subject’s welfare or behavior.

6. **Source of Participants:** Only participants recruited under the Consortium of Addiction Research (CAR) will be recruited.
7. **Identification of Potential Participants:** Only participants recruited under the Consortium of Addiction Research (CAR) and referred to our study by the CAR will be recruited. Participants will **not** be recruited based on information contained in private/protected records (e.g., medical records, student records; note that this also includes participants who will be recruited from the PI's or Co-PI's patient or student population.)
  1. No private/protected records will be used.
  2. Potential participants will self-identify and express their interest after learning about the study through the CAR registry.
  3. No **MEDICAL** records will be used.
  4. HIPAA form states that the participant does agree to have research staff communicate with treatment program staff that they are participating in research so that they know their whereabouts during their break time.
8. **Recruitment Materials:** Only participants recruited under the Consortium of Addiction Research (CAR) and referred to our study by the CAR will be recruited.
9. **Payment:** There is no cost for the participant to be in the study. Participant will be compensated at the end of each of each day of participation (8 potential days plus three follow-up timepoints). Participants will be compensated \$25 for Baseline questionnaires completed; \$25 at the end of the second MRI scan; \$10 for tDCS interventions days 1-5; \$25 on MRI #2 for questionnaires completed; and \$25 for the scan. For the first follow-up timepoint the participant will be compensated with \$100 (\$50 for the questionnaires/assessment session and \$50 for the MRI scan). For the second and third follow-up timepoints, the participant will be compensated with \$100. To summarize, if a participant completes all participation days, they can receive up to \$450 for participating in this study. Additionally, if participants choose to complete the optional Websurf task (~30 minutes), they will be compensated with \$20 for each task completion (Participants can complete this task up to three times during their participation in this study). If participants choose to complete the daily optional Ecological Momentary Assessment survey during their visits while they are in the treatment program, they will receive \$1 per completed EMA assessment. (*EMA payment will be given weekly and these payments will be processed*

*on the business day following each 7-day window. At each weekly EMA payment during the follow-up period, participants will get a \$5 bonus if they have completed at least 2 EMA assessments per day in the past week). If participants choose to complete the wearable device optional portion of the study, they will receive \$80. All compensation will be awarded through a reloadable Greenphire ClinCard.*

Parking expenses up to \$7 will be reimbursed to the participant if they need to pay parking at each in-person follow-up visit.

*No Research Experience Points will be awarded.*

## 1. **Risks to Participants**

1. Foreseeable Risks: tDCS is considered to be a non-invasive investigational device that involves applying a weak electrical current to the scalp. This device has been labeled as a non-significant risk device by the FDA for investigational purposes. There is currently no evidence of serious side-effects. Mild side-effects that typically resolve upon discontinuing tDCS include light itching under the electrode at the beginning of administration, headache, fatigue, and nausea. The subject may choose to discontinue stimulation at any time during the session if experiencing excessive discomfort or side effects. Although seizures are not a known risk of tDCS intervention (Fregni et al., 2006), anyone with a history or a risk for seizures will be excluded from the study. No other risks related to tDCS are anticipated. To minimize risks regarding tDCS, study staff will be using standards of administration that have been shown as safe in numerous other studies using transcranial direct current stimulation. The length of administration of the current, size of electrode sponges used, and method of applying stimulation are the same as methods of administration that have been demonstrated as safe.
2. The other potential risks pertain to the maintenance of confidentiality. Participants will be probed for personal information during the interviewing process. As noted in the consent form, participants will be told that all diagnostic and other sensitive raw data will be kept in a locked file and available only to authorized investigators involved in this study. To minimize confidentiality risks, as noted in the consent form, all diagnostic and other sensitive raw data will be kept in a locked file and be available only to authorized investigators involved in this study. Genetic and epigenetic information will be for research purposes only and will not be included in participants' medical records. Genetic specimens and data will be labeled with the participant's study ID number and will not contain personally identifying information. Confidentiality is not absolute. Research staff are mandated reporters and are legally required to report suspicion of child or vulnerable adult abuse or neglect to the relevant authorities.
3. MRI risks. Individuals will complete a screening questionnaire for contraindications of MRI scanning. Any affirmative responses on the questionnaire will result in an interview regarding the possible contraindication. An attempt will be made to secure any records of the nature of the possible contraindication and this information will be reviewed by the PI and CMRR staff at the University of Minnesota. A determination

will be made regarding the level of risk to the subject and whether they are approved for scanning. If approved for scanning by professionals, all risks to the subject will be conveyed to him or her so they can deliberate as to whether or not they want to complete the procedure. Any concerns from the review committee will be conveyed to the participant at that time. If the subject has certain problematic iron or steel implants in their body that cannot be removed, the subject may not have the scan and will be excluded from that part of the study.

1. There are no known risks to humans due to the static magnetic field. Subjects, operators, and guests are carefully screened prior to entering the magnetic environment, and frequently reminded of the potential danger of introducing magnetic objects to the controlled area. Subjects are carefully screened and excluded from the study if they have any implanted devices. Subjects are always accompanied when near the magnet, and reminded to move slowly and carefully as they enter and leave the magnet.
2. The risk of tissue damage by energy emitted by the MRI device is controlled by compliance with FDA guidelines for commercial MRI devices. Safety devices are in place so that the magnet will cease to operate should any parameters begin to exceed their preset safety limits. The risk of peripheral nerve stimulation by  $dB/dt$  is limited by safety devices. The noise levels generated by each scan are monitored to ensure adherence to guidelines. In addition, subjects are provided with earplugs and secondary protection (foam covering or headphones) to increase comfort during the scan.
3. Reproduction Risks: Since the MRI risks to fetuses are unknown, pregnant women are excluded from the study. Female subjects in child-bearing years will be informed that their consent to participate indicates that they are willing to complete a urine pregnancy test to demonstrate that they are not pregnant.
4. Risks to Others: N/A.

## **15. Potential Benefits to Participants**

1. Potential Benefits: There is no direct benefit to you to participate in this study. Learning more about brain function in psychiatric disorders could aid in directing patient treatment in the future.

## **16. Data Management**

1. Data Analysis Plan: A mixed model analysis of variance will be conducted with between-group measures (sham vs active tDCS) and within-group measures (FC and craving reports before and after cognitive flexibility training and tDCS intervention). This mixed model analysis will examine main effects and interaction effects. To examine the long-term effects of cognitive flexibility training and tDCS, we will conduct a repeated measures analysis using longitudinal data collected monthly for 6 months after intervention completion. A Log-rank (Mantel-Cox) Test (used in Klaus et al 2014) will be conducted to establish the efficacy of cognitive flexibility training and active tDCS vs. cognitive flexibility training and sham tDCS in the time domain.
2. Power Analysis: The study in reference is a pilot study for which a power analysis is not applicable.
3. Data Integrity: The principal investigator and co-investigator will monitor data quality for this study. They will ensure that data are generated, documented (recorded), and reported, in compliance with this protocol, with Good Clinical Practice, and any other applicable regulatory requirements.

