### **3. Study Endpoints/Events/Outcomes**

1. Primary Endpoint/Event/Outcome: In a double-blind randomized design, 100 abstinent (~2 weeks abstinent) individuals with alcohol use disorder (AUD) recruited from Lodging Plus Program will receive 10 sessions (2 sessions per day for 5 days) of either (i) transcranial direct current stimulation (tDCS) to the PFC or (ii) sham-tDCS. All subjects will perform the reversal learning task during tDCS intervention (active or sham) to prime the engagement of the NAcc-PFC brain circuit that mediates cognitive flexibility. Rest fMRI and craving measures will be collected before the first and after the last day of tDCS sessions, and about one month after the last fMRI (timepoint depending on participant availability). Monthly follow-up interviews will be conducted for approximately 8 months after intervention completion to query relapse status. Dependent variables will be (i) change in NAcc-PFC FC between 2,3 weeks of abstinence and one month later, (ii) change in craving scores between 2 and 3 weeks of abstinence and (iii) relapse status ~8 months after study participation. Aim 1: To investigate whether NAcc-PFC FC can be modulated, we will compare magnitude and durability of change in NAcc-PFC FC between active-tDCS and sham-tDCS groups. Aim 2: To determine if PFC stimulation has a short-term effect on behavior related to clinical outcome, we will compare change in craving scores (difference in craving scores between 2 and 3 weeks of abstinence) between active-tDCS and sham-

tDCS groups. Aim 3: To correlate neuromodulation intervention with long-term clinical outcome, we will record craving and relapse status during the ~8 months following treatment discharge. We will examine the relationship between change in NAcc-PFC FC between 2 and 3 weeks of abstinence and subsequent (i) monthly craving scores and (ii) relapse status. Aim 4: Examine relationships between genetic variants, epigenetic changes and treatment outcome (e.g. durability, functional connectivity).

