## 1. Procedures Involved

1. Study Design: This study is double-blind, within subject, and sham-controlled. The scientific integrity of the trial and the credibility of the data from the trial depend substantially on the trial design. A description of the trial design includes: In a double-blind randomized design, 100 abstinent (approximately 2 weeks abstinent) individuals with alcohol use disorder (AUD) recruited from Lodging Plus Program will receive 10 sessions (2 sessions per day for 5 days) of either (i) active transcranial direct current stimulation (tDCS) to DLPFC or (ii) sham-tDCS. All subjects will perform the reversal learning task during tDCS intervention (active or sham) to prime the engagement of the NAcc-PFC brain circuit that mediates cognitive flexibility (D'Cruz et al., 2011). Rest fMRI and craving measures will be collected before the first and after the last day of tDCS sessions. Follow-up interviews will be scheduled for each month, but may not happen exactly every month, depending on the participant's availability. Follow-ups will be conducted for approximately 8 months after study completion to query relapse status. Dependent variables will be (i) change in NAcc-DLPFC FC between 2 and 3 weeks of abstinence, (ii) change in craving scores between 2 and 3 weeks of abstinence and (iii) monthly queries on relapse status for the next 6 months after intervention completion. Aim 1: To investigate whether NAcc-DLPFC FC can be modulated, we will compare magnitude of change in NAcc-DLPFC FC between active-tDCS and sham-tDCS groups. Aim 2: To determine if DLPFC stimulation has a short-term effect on behavior related to clinical outcome, we will compare change in craving scores (difference in craving scores between 2 and 3 weeks of

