3. Participants who consent to the study and meet study criteria as per the screening evaluation will be asked to participate in an 8-day session study, be available for monthly phone follow-up measures after study completion to query relapse status and for 3 in-person (or remote) follow-up visits. At any of the in-person follow-up visits, research staff may test participants for recent alcohol use using a Breathalyzer (will not be administered if assessments are remote). Participants will be informed of alcohol level, but will not be excluded from the study if test shows recent alcohol use. If Breathalyzer shows alcohol level of > 0.08%, participant will be asked to reschedule visit. While the target will be to conduct follow-up phone calls every month, plus in-person/remote assessments at 1, 4 and 8 months

timepoints, the actual date for these follow-up sessions will vary depending on participant availability.

The participants who are referred to our study by the Consortium of Addiction Research (CAR; approved under IRB protocol #STUDY00005170) will be asked if they are interested in participating. Participants will be informed about the study via the “1406M51241 Invite,” which informs them that they need to be available for 8 appointments during their stay at the treatment program. They also need to be available for monthly (depending on subject availability) phone follow-up measures after study completion to query relapse status and for the 3 in-person (or remote) follow-up visits.

**Baseline Interview:** A research staff member will meet the participant either in person or through a virtual video conference to complete the informed consent process with the participant and administer surveys assessing behavior, personality and substance use, and alcohol craving levels. Understanding of informed consent will be assessed with the “Assessment of Informed Consent” form. Participants will also complete a screening questionnaire for contraindications of MRI scanning. Females who could potentially be pregnant will be tested for pregnancy and, if positive, will not be allowed to participate. If testing is refused, participation will not be allowed. Baseline assessments will take about 1.5 hours total.

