The subject indicates his decision by touching one of the two square response panels, located at the bottom of the display, containing the associated “stake” written in either red or blue ink. Immediately after a selection, one of the boxes opens to reveal the location of the token, accompanied by either a “You win!” or a “You lose!” message written in large yellow font. If the subject chooses the correct color, the stake associated with that color is added to the total points score; if the subject chooses the wrong color, the same stake is subtracted. No monetary significance is attached to the points accumulated by the end of the task. At the start of each sequence, the subject is given 100 points and instructed to make whatever choices thought necessary to increase this score by as much as possible. It is emphasized that these choices might involve either conservative or risk-taking behavior. The ratio of colored boxes (5:1, 4:2, and 3:3) and the balance between the associated rewards

(10 vs 90, 20 vs 80, 30 vs 70, 40 vs 60, and 50 vs 50) vary independently from trial to trial according to a fixed pseudorandom sequence. This sequence ensures that each balance of reward and each ratio of colored boxes co-occurs an equal number of times, with the restriction that on all trials with an unequal ratio of red and blue boxes (i.e., 5:1 or 4:2), the larger reward is always associated with the least likely outcome (i.e., the color with the fewest number of boxes; see Figures A and B), thus capturing the conflict inherent in risk-taking situations.

After the last tDCS day, the participant will be given the same behavior, personality, craving and substance use questionnaires as baseline.

MRI #2: Follow-up MRI scan with the same procedures as baseline will be collected. Total participation time for MRI #2 will be about 3 hours.

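### Section 16.1 tests short-term FC and craving on raw before/after change; adjusting for the baseline already collected costs at most about 1.5% efficiency at 70 pairs and may gain much more

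*Combined protocol and SAP*

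**What the plan says.** Section 16.1 (Data Analysis Plan) sets the analysis: "A mixed model analysis of variance will be conducted with between-group measures (sham vs active tDCS) and within-group measures". The within-participant measures are FC and craving reports before and after the training and tDCS. It adds: "This mixed model analysis will examine main effects and interaction effects". No effect is singled out as the test of active against sham, and no baseline covariate appears there or elsewhere in the document. Section 16.1 also does not say whether the mixed model is an ANOVA on complete pairs or a likelihood fit that keeps incomplete ones.

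The aims are worded as comparisons of change. In Section 5 (Procedures Involved), Aim 1 reads: "we will compare magnitude of change in NAcc-DLPFC FC between active-tDCS and sham-tDCS groups". In Section 3, Aim 2 reads: "we will compare change in craving scores (difference in craving scores between 2 and 3 weeks of abstinence" (that is, active against sham).

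Baseline values of both outcomes are scheduled. Section 5 says: "Rest fMRI and craving measures will be collected before the first and after the last day of tDCS sessions". It also repeats the questionnaires after the intervention: "After the last tDCS day, the participant will be given the same behavior, personality, craving and substance use questionnaires as baseline".

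On sample size, Section 16.2 says: "The study in reference is a pilot study for which a power analysis is not applicable". Section 25 expects complete data on 70 participants from about 100 consented.

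**The concern.** A two-arm, two-time-point mixed ANOVA treats the baseline value as an outcome. Its interaction compares raw change, which fixes the slope of post on pre at 1. Adjusting for baseline estimates the slope that minimises the variance. Unless the true slope happens to be close to 1, the raw-change comparison discards information that the trial has already paid to collect.

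What is at stake is the width of the confidence intervals for the short-term active-versus-sham comparisons of FC (MRI #1 to MRI #2) and craving. With no power target in Section 16.2, no planned margin offsets avoidable imprecision. Validity is not at stake, because randomisation makes both estimators unbiased.

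A smaller point follows from examining main effects and interactions together. The arm main effect averages the pre and post values, so it is not the comparison that Aims 1 and 2 describe.

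**Working it through.** **Inputs from the documents.** Two arms with a 50% chance of each (Section 5); one pre and one post value for FC and craving (Sections 3 and 5); 70 participants with complete data from about 100 consented (Section 25). The 70 refers to completing the whole study of about 8 months. Both short-term measurements fall within the residential stay: participants are told "they need to be available for 8 appointments during their stay at the treatment program", which matches 1 baseline + 1 MRI + 5 intervention days + 1 MRI = 8. The number of short-term pairs may therefore lie between 70 and 100, and I use both ends.

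**Inputs not in the documents.** Pre-post correlation r, SDs and effect size. Every gain below is conditional on assumed values.

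**The plan's own figure.** Section 25 gives 25% attrition. 100 × 0.75 = 75, not 70; and 70 / 0.75 = 93.3, so 94 rather than 100. That mismatch is a separate matter and does not affect this point (see the penalty at 75 pairs below).

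**Step 1: the planned interaction is the change-score test.** With complete pairs, the arm-by-time F equals the squared t on change. On a simulated data set with 35 per arm, both were 3.1376.

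**Step 2: large-sample variances.** Set SD_pre = 1 and k = SD_post/SD_pre, with 1:1 arms.
- Raw change: variance proportional to 1 + k² − 2rk
- Adjusted for baseline: proportional to k²(1 − r²)
- Difference (change minus adjusted): (1 − rk)², which cannot be negative

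**Step 3: price of estimating the slope.** The adjusted variance is multiplied by 1 + 1/(N − 4): 1 + 1/66 = 1.0152 at 70 pairs, 1 + 1/71 = 1.0141 at 75, and 1 + 1/96 = 1.0104 at 100. The worst case is rk = 1, where adjustment gains nothing: 1/1.0152 − 1 = −1.5% at 70 and 1/1.0104 − 1 = −1.0% at 100.

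**Step 4: net gain in effective sample size** = (1 + k² − 2rk) / [factor × k²(1 − r²)] − 1. For example, k = 1, r = 0.5, 70 pairs: 1 / (1.0152 × 0.75) − 1 = 31%.

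| Assumed setting | r = 0.3 | r = 0.5 | r = 0.7 | r = 0.9 |
|---|---|---|---|---|
| k = 1, 70 pairs | 52% | 31% | 16% | 4% |
| k = 1, 100 pairs | 52% | 32% | 16% | 4% |
| k = 1.25, 70 pairs | 26% | 10% | 0.4% | 4% |
| k = 0.8, 70 pairs | 96% | 72% | 57% | 62% |

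At equal SDs, 70 adjusted pairs are worth about 106, 92, 81 and 73 pairs analysed by raw change. Break-even at 70 pairs is near r = 0.97.

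**Step 5: expected 95% CI half-width** in SD units, equal SDs, raw change against adjusted.

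| Pairs | r = 0.3 | r = 0.5 | r = 0.7 | r = 0.9 |
|---|---|---|---|---|
| 70 | 0.564 vs 0.459 | 0.477 vs 0.416 | 0.369 vs 0.343 | 0.213 vs 0.210 |
| 100 | 0.470 vs 0.381 | 0.397 vs 0.346 | 0.307 vs 0.285 | 0.177 vs 0.174 |

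**Step 6: check by simulation.** With 40,000 replicates per setting at 35 per arm, the variance ratios (adjusted/change) at r = 0.3, 0.5, 0.7 and 0.9 were 0.66, 0.76, 0.87 and 0.96, against 0.66, 0.76, 0.86 and 0.96 from the formula. With a true slope of 1 the ratio was 1.014 to 1.016, and 1.015 with a skewed baseline.

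**Step 7: incomplete pairs.** Assumed: 100 randomised 1:1, 75 complete, 20 lacking the post value, 5 lacking the baseline, missing completely at random, 6,000 replicates per cell. Variance relative to a longitudinal model with a common baseline mean, at r = 0.3, 0.5, 0.7, 0.9:

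| Analysis | k = 1 | k = 1.25 |
|---|---|---|
| Raw change, complete pairs | 1.59, 1.37, 1.19, 1.05 | 1.33, 1.17, 1.04, 1.06 |
| Group × time likelihood fit, baseline means free | 1.44, 1.28, 1.14, 1.03 | 1.22, 1.10, 1.01, 1.02 |
| Linear model on baseline, complete pairs | 1.05, 1.05, 1.03, 1.01 | 1.05, 1.06, 1.04, 1.02 |

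The common-baseline model was the most precise in all 8 cells. All estimators averaged 0.296 to 0.301 against a true effect of 0.30.

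**The case against.** **This is a pilot and the planned test is valid.** Both true. No stated power claim fails, and at r = 0.9 with equal SDs the half-width moves only from 0.213 to 0.210. That limits how strongly the point can be pressed. Even so, the trial compares arms on these outcomes, and the choice is lopsided: a loss of about 1.5% at worst against a possible double-digit gain.

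**The precision result has a condition.** It needs equal arms or a common baseline slope. With assumed slopes of 1.3 and 0.7, the simulated variance ratio (adjusted/change) was about 1.02 at 35/35 and 1.04 to 1.05 at 28/42, and with residual SD 0.5 it was still about 1.03 at 280/420. The condition stands. The planned 1:1 allocation meets it, and departures cost little even under that strong slope difference.

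**Section 16.1 does not use the words raw change, and a mixed model might keep incomplete pairs.** Fair. The equivalence needs complete pairs. Under a likelihood fit, a simple linear model on complete pairs can do worse: about 3% less precise in one simulated cell (k = 1.25, r = 0.7). The fix therefore offers the common-baseline longitudinal model.

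**The third scan might be a further level of the time factor.** Section 3 mentions FC one month later. If that scan were included, the FC interaction would no longer be the two-point test and the FC figures above would not describe it. The before/after wording of 16.1 and Aim 1 in Section 5 make two levels the natural reading, and craving under Aim 2 is unaffected.

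**Conclusion.** The point holds. As written, the short-term FC and craving comparisons rest on raw change, and baseline adjustment would use data already scheduled to answer the same between-arm question. It should be changed, but as a matter of efficiency, not of bias or invalidity.

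The size of the gain cannot be known from the documents. Over the assumed grid at 70 pairs it runs from 0.4% to 96%, with a floor of about −1.5% (−1.0% at 100 pairs). These figures rest on 1:1 arms or a common slope, complete pairs, and the before/after comparison only. They say nothing about the monthly follow-up or the one-month scan.

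**What to change.** In Section 16.1:

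- Name as the short-term Aim 1 and Aim 2 test the arm coefficient, with 95% CI, from a linear model of the post-intervention value (FC at MRI #2; post-intervention craving) on arm and the participant's own baseline value.
- If participants with only one of the two values are to be kept, use instead the equivalent longitudinal model with a common baseline mean for both arms.
- State that main effects are not the test of active against sham.
- If the one-month FC comparison is added to address durability, adjust it for baseline FC and include a baseline-by-time term. This is secondary and not quantified here.

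The cost is a short paragraph, slight extra analysis work, one degree of freedom, and about 1.5% of variance at 70 pairs (1.0% at 100) for estimating the slope. No new data, visits or participants are needed.
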